Descriptive statistics will be presented on the change from Baseline to Week 8 in PANSS total score and subscale scores, CGI-S score, BNSS total score, PSP total score, PSQI global score, SF-12 score, and MSQ score. For CGI-I score, descriptive statistics by visit, including Week 8, will be presented.

Descriptive statistics by visit will be presented for the HCRU. The frequency and percentage of subjects with physician office visits, ER visits, hospitalizations at Baseline and at each post-Baseline

scheduled visit will be summarized. The change in the number of physician's office visits, ER visits, and hospitalizations per month, the average length of hospital stays, and the average number of hours a caregiver spends per week helping the subject from Baseline at each post-Baseline scheduled visit will be summarized.

Subgroup analyses will be described in the statistical analysis plan (SAP).

Sample Size:

Approximately 120 subjects will be required for this study. This sample size was determined by the width of the 95% confidence interval for the proportion of subjects who may discontinue due to clinical reasons by Week 8 to ensure the precision of the estimate of the true discontinuation treatment failure rate due to clinical reasons. Assuming 1) 15% of SEP-363856 treated subjects will experience discontinuation due to clinical reasons by Week 8 and 2) 6.4% as the half width (the distance between the upper/lower limits to the point estimate) of the 95% confidence interval (ie, [8.6%, 21.4%]), approximately 120 subjects will be required.

Table 2: Schedule of Assessments

	Screening Period	Treatment Period										Follow-up Period
		V1	V2	V3	V4	V5	V6	V7	V8	V9	V10	
Study Day ^e	Screening ^a	Pre-switch Baseline	Week 1	Week 2	Week 3	Week 4	Week 5	Week 6	Week 7 TC	Week 8 ^b EOT/ET ^c	Week 9 ^d Follow-up	
	Days -21 to -1	Day 1	Day 8	Day 15	Day 22	Day 29	Day 36	Day 43	Day 50	Day 57	7 ± 2 days after last dose	
	Informed consent	X										
Informed consent for duplicate subject check	X											
CCI												
Review inclusion/exclusion criteria	X	X										
Prior/concomitant medication review	X	X	X	X	X	X	X	X	X	X	X	
Dispensation of study drug ^g		X	X	X	X	X	X	X				
Study drug accountability			X	X	X	X	X	X		X		
Demography	X											
Medical history	X											
Psychiatric history	X											
Nicotine use information	X									X		
SCID-5-CT ^h	X											
Physical and neurological examination	X									X	X	
Height	X											

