- j. BMI will be calculated and recorded in the eCRF by the clinical site at screening. For other visits, BMI will be derived in the EDC system.
- k. Subjects must be fasted (no food or drink except water at least 8 hours prior to specified blood tests) at Pre-switch Baseline (Visit 2) and Week 8/EOT/ET (Visit 10). Fasting for 8 hours prior to Screening (Visit 1) is also recommended to avoid potential retests. Blood samples should be drawn in the morning followed by a snack or meal. A list of clinical laboratory tests is provided in [Section 23](#).
- l. Blood samples for follicle stimulating hormone (FSH) will be collected for post-menopausal women or if menopause is suspected.
- m. Any positive urine β -hCG test should be confirmed by a serum β -hCG test.

C [REDACTED] **C** [REDACTED] Blood samples for determination of plasma SEP-363856 concentrations will be collected predose (prior to administration of the first dose) on Day 1; 3 additional samples will be collected on Days 8, 29 and 57/ET. The time and date of the previous dose of study drug and the time and date of blood sampling must be recorded. The remaining plasma samples, after PK measurement is completed, **CCI** [REDACTED].

- p. Positive urine drug screen (UDS) results should be discussed with the Medical Monitor.
- q. Unscheduled SAS, BARS and AIMS scales should be administered if a subject develops extrapyramidal symptoms (EPS) requiring treatment.
- r. Healthcare resource utilization questions are described in [Section 11.5.8](#). Baseline will have 3-month lookback period. Week 8/ET will be since last assessment.
- s. Events occurring prior to first dose of study drug are pretreatment events. Events occurring after first dose of study drug are adverse events. Determination done programmatically.
- t. Where local regulations allow, duplicate subject check will be performed. Following the last contact with a subject, the duplicate enrollment system should be updated, as appropriate.

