11.5.8. Healthcare Resource Utilization

Healthcare resource utilization will be assessed by recording the following at Baseline:

- Number of physician office visits, emergency room visits, and hospitalizations (total number and number related to schizophrenia) in the previous 3 months
- Length of each hospital stay in the past 3 months
- Employment status in the past 3 months
- The average number of hours a caregiver(s) spends helping the subject per week (past 3 months)

Healthcare resource utilization will be assessed by recording the following post Baseline:

- Number of physician office visits, emergency room visits, and hospitalizations (total number and number related to schizophrenia) since prior assessment
- Length of each hospital stay since prior assessment
- Employment status since prior assessment
- The average number of hours a caregiver(s) spends helping the subject per week (since prior assessment)

[figure not shown]

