11.9.8. Visit 8 (Week 6; Day 43 \pm 2 days) – Treatment Period

The following procedures will be conducted during this visit:

- Collect concomitant medications
- Vital sign measurements
- PANSS
- CGI-S
- CGI-I
- C-SSRS
- Collect adverse events

- Study drug accountability
- Dispense study drug

11.9.9. Visit 9 Telephone Contact (Week 7; Day 50 ± 2 days) – Treatment Period

The following procedures will be conducted during this visit:

- Collect concomitant medications
- C-SSRS
- Collect adverse events

11.9.10. Visit 10, End of Treatment (EOT) or Early Termination (ET) - (Week 8; Day 57 ± 2 days)

The following procedures will be conducted during this visit:

- Collect concomitant medications
- Collect nicotine use information
- Physical and neurological examination
- Vital sign measurements
- Weight and waist circumference (BMI derived in the electronic data system)
- Perform standard 12-lead ECG
- Fasted blood samples for clinical laboratory evaluation (hematology and serum chemistry) and β -hCG (for female subjects)
- Blood sample for POPPK
- Urine sample for urinalysis, rapid urine β -hCG (females), rapid urine drug screen, and UDS
- PANSS
- CGI-S
- CGI-I
- BNSS
- PSQI
- C-SSRS
- SAS
- BARS
- AIMS
- SF-12
- MSQ

- PSP
- HCRU (since last visit)
- Collect adverse events
- Study drug accountability
- Duplicate subject check

At this visit, subjects who have participated throughout the duration of the Treatment Period, up to and including Week 8 will have the option to enroll and continue treatment in an open-label extension study (Study SEP361-309).

For subjects entering the extension study, the Week 8 Visit in this study (SEP361-308) will serve as the OLE Baseline visit for the extension study (SEP361-309) and subjects will not need to return for further visits in this study.

Subjects who do not enter the extension study will complete the Follow-up Period.

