15.3.6.1. Healthcare Resource Utilization

The number of physician's office visits, ER visits, and hospitalizations (for any reason and those related to schizophrenia) per month at Baseline and at Week 8, as well as the average length of hospital stays (for any reason and those related to schizophrenia), will be summarized. The frequency and percentage of subjects receiving unpaid care at each time point, along with the average number of hours a caregiver spends per week helping the subject, will also be summarized.

The change in the number of physician's office visits, ER visits, and hospitalizations, the average length of hospital stays, and the average number of hours a caregiver spends per week helping the subject from Baseline at Week 8 will be summarized. Shifts from Baseline to Week 8 in whether the subjects receive unpaid care will also be summarized.

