6.7. COMMON CALCULATIONS

For quantitative measurements, change from Baseline will be calculated as:

- Test Value at Visit X - Baseline Value

For PANSS total score, percentage change from Baseline will be calculated as:

- $(\text{Test Value at Visit X} - \text{Baseline Value}) \times 100 / (\text{Baseline Value} - 30)$

For other quantitative measurements, percentage change from Baseline will be calculated as:

- $(\text{Test Value at Visit X} - \text{Baseline Value}) \times 100 / \text{Baseline Value}$

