16.8. HEALTHCARE RESOURCE UTILIZATION

Healthcare resource utilization is assessed at these study visits: Visit 2 and Visit 10.

The number of physician's office visits, ER visits, and hospitalizations (for any reason and those related to schizophrenia) per month at Baseline and at Week 8/Visit 10, as well as the average length of hospital stays (for any reason and those related to schizophrenia) at Baseline and at Week 8/Visit 10, will be summarized. The frequency and percentage of subjects receiving unpaid care at Baseline and at Week 8/Visit 10, along with the average number of hours a caregiver spends per week helping the subject, will also be summarized.

The change in the number of physician's office visits, ER visits, and hospitalizations, the average length of hospital stays, and the average number of hours a caregiver spends per week helping the subject from Baseline at Week 8/Visit 10 will be summarized.

Shift from Baseline to Week 8/Visit 10 in whether the subjects receive unpaid care will also be summarized.

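### Does dropping per month from the healthcare-use change sentence turn the analysis into a 3-month count set against an 8-week count?

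*SAP*

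**What the plan says.** Healthcare resource utilization (HCRU) is listed among the other endpoints and is summarized descriptively. SAP 16.8 places it at Visits 2 and 10 only. Protocol Table 2, footnote r, sets the recall periods: "Baseline will have 3-month lookback period. Week 8/ET will be since last assessment". Protocol 11.5.8 agrees, collecting post-Baseline "hospitalizations (total number and number related to schizophrenia) since prior assessment". The Visit 10 checklist in Protocol 11.9.10 is looser: "HCRU (since last visit".

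The analysis text comes in pairs, a sentence on levels and then a sentence on change:

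- SAP 16.8, levels: counts "per month at Baseline and at Week 8/Visit 10, as well as the average length of hospital stays". Change: "The change in the number of physician's office visits, ER visits, and hospitalizations, the average length of hospital stays", with no mention of a month.
- Protocol 15.3.6.1, levels: counts "per month at Baseline and at Week 8, as well as the average length of hospital stays". Its change sentence drops the month in the same way.
- Protocol synopsis, change: "ER visits, and hospitalizations per month, the average length of hospital stays".

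SAP 6.7 gives the general change formula, "Test Value at Visit X - Baseline Value". SAP 6.4 moves early-termination (ET) measurements to the next visit at which that assessment was due, which for HCRU is always Week 8. SAP 16.9 sets a month at 30 days, but only for converting cigarette use. Neither document writes a formula for the HCRU monthly number.

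**The concern.** The two recall windows are unequal by design. If the change sentence in SAP 16.8 is read alone and passed through the SAP 6.7 formula, a count over roughly 56 days has a count over 3 months subtracted from it, and use appears to fall even when nothing has changed. Early terminators make this worse, because their shorter windows are also filed under Week 8. The study has no control arm in which the same artefact would show up, the impact on HCRU is a stated objective, and for most of these items the error would flatter the drug. Even with the monthly reading, the plan does not say what the Week 8 count is divided by.

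**Working it through.** **Inputs.** Visit 2 is Day 1 and Visit 10 is Day 57 ± 2 (Protocol Table 2), so a completer's window is 57 − 1 = 56 days, range 54 to 58. The Baseline window is 3 months. An ET visit at the Week 4 visit day has a window of 29 − 1 = 28 days. Assumptions: constant true use of 1 visit per month, and a month of 365.25/12 = 30.4375 days. The plan states no HCRU figure, so there is nothing to reproduce first.

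**Step 1: raw-count reading.** Baseline count = 3. Post-Baseline count = days/30.4375.

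| Window (days) | Post count | Change in count | Percent |
|---|---|---|---|
| 56 | 1.840 | −1.160 | −38.7% |
| 54 | 1.774 | −1.226 | −40.9% |
| 58 | 1.906 | −1.094 | −36.5% |
| 28 (ET) | 0.920 | −2.080 | −69.3% |

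The arithmetic of the worry is right for this reading.

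**Step 2: which reading the text supports.** In SAP 16.8 the levels are monthly numbers at Baseline and at Week 8. The next paragraph asks for the change in the number of the same items between the same two time points. SAP 6.7 subtracts one analysed value from another. If the analysed value is the monthly number, the result is a monthly change. SAP 6.7 therefore does not favour raw counts; it takes whatever value the section has defined. The synopsis says the change is per month.

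**Step 3: monthly reading.** Baseline rate = 3/3 = 1. Post-Baseline rate = count/(days/m), where m is days per month. With m = 30.4375 the rate is 1 for every window, so the change is 0. With m = 30 the rate is 30/30.4375 = 0.986, a change of −0.014 per month.

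**Step 4: how much the unwritten divisor matters.** The Baseline divisor is plainly 3, because the lookback is 3 months. After Baseline:

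- Completer with one visit in 56 days: 30/56 = 0.536 per month or 30.4375/56 = 0.544. The choice of month length is immaterial.
- A fixed divisor of 2 months at constant use: 1.840/2 − 1 = −0.08 for a completer, but 0.920/2 − 1 = −0.54 for a 28-day ET window.
- Effect on the mean if a share f left at 28 days: −0.54f − 0.08(1 − f). For f = 7.2% this is −0.039 − 0.074 = −0.113. For f = 15% it is −0.081 − 0.068 = −0.149. These shares are the two rates of discontinuation for clinical reasons quoted in SAP 3.4, used here only as assumed values of f. The all-cause share is not given and could be larger.

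A fixed 2-month divisor would be a poor choice. Elapsed days is the natural one, since the question asks about the time since the prior assessment and both visit dates are on file.

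**Step 5: would a mistake stay hidden?** For subjects with both assessments, the mean change must equal the Week 8 mean minus the Baseline mean. At constant use, monthly levels would read 1.0 and 1.0 while a raw-count change read about −1.16. Both come from SAP 16.8, so the contradiction would be plain in the output.

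**Step 6: recall wording.** Protocol 11.9 opens by sending the reader to Table 2 for the procedures at each visit and to Sections 11.1 to 11.7 for how to conduct them. Footnote r and Section 11.5.8 both refer to the previous assessment, and the only earlier HCRU assessment is Visit 2. The checklist line is shorthand.

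**The case for a change.** The strongest case for acting is that the fix is nearly free and the error, if made, is large and favourable to the drug. The protocol itself carries both wordings, so the statement in SAP 3.7 that nothing departs from the protocol cannot settle which one governs. Adding the missing phrase would still leave the divisor open, and Step 4 shows that a careless divisor distorts early terminators' rates. A site that followed the Visit 10 checklist literally could also have asked about the wrong period.

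Some of this stands. The phrase is missing from two change sentences, the post-Baseline divisor is not written anywhere, and SAP 3.7 is not decisive alone.

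The rest does not carry. The 36% to 41% and 69% falls require reading one sentence apart from the paragraph before it and against the synopsis. The lack of a control arm does not conceal the artefact, because the monthly levels expose it. The recall conflict is between a one-line checklist entry and the two places that define the assessment. Eligibility also lowers Baseline use: the criteria on clinical stability and on no recent psychiatric hospitalization reduce schizophrenia-related events in the lookback. That is a separate matter of interpretation which no rescaling would remove, and it is not a fault in SAP 16.8.

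**Conclusion.** No change follows. This is a phrase not repeated and a derivation detail left to programming, for a descriptive endpoint that does not touch the primary or secondary results. Analysts who must produce monthly levels at both time points already have to build the monthly rate, and the change follows from it by subtraction. With elapsed time in the divisor, the artefact at constant use is 0, or −0.014 per month if a month is taken as 30 days. The one choice with real effect is a fixed 2-month divisor, which would give −0.08 per month for completers and −0.54 for a 28-day early terminator at 1 visit per month. Nothing in the plan calls for that divisor.

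The conclusion rests on three assumptions: that the HCRU form asked about the time since the Visit 2 assessment, as footnote r and Protocol 11.5.8 state; that the programmers divide by elapsed time; and that the table templates cited in SAP 8, which are not part of the documents reviewed, do not specify a raw-count difference.

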5.3. Other Objectives

- To evaluate the tolerability and safety of switching clinically stable outpatients with schizophrenia from a typical or atypical antipsychotic to SEP-363856 over a period of 8 weeks using:
 - Adverse event reports
 - Clinical laboratory tests
 - Vital sign measurements
 - 12-lead electrocardiograms (ECG)
 - Columbia – Suicide Severity Rating Scale (C-SSRS)
 - Barnes Akathisia Rating Scale (BARS)
 - Abnormal Involuntary Movement Scale (AIMS)
 - Simpson-Angus Scale (SAS)
- To evaluate the effectiveness of SEP-363856 using:
 - Positive and Negative Syndrome Scale (PANSS)
 - Clinical Global Impression-Severity (CGI-S) scale
 - Clinical Global Impression-Improvement (CGI-I) scale
 - Brief Negative Symptom Scale (BNSS)
- To evaluate the effects of SEP-363856 on health-related quality of life as measured by the Short Form Health Survey (SF-12)
- To evaluate the effects of SEP-363856 on functional capacity as measured by the Personal and Social Performance Scale (PSP)
- To evaluate medication satisfaction as measured by the Medication Satisfaction Questionnaire (MSQ)
- To evaluate sleep as measured by the Pittsburgh Sleep Quality Index (PSQI)
- To evaluate the impact of SEP-363856 on healthcare resource utilization (HCRU)

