8. SELECTION OF SUBJECTS

8.1. Subject Inclusion Criteria

To qualify for participation, subjects must meet all of the following inclusion criteria:

1. Subject must give written informed consent and privacy authorization prior to participation in the study. Separate consent will be obtained from a caregiver or legal guardian if required by local law.
2. In the Investigator's opinion, the subject is appropriate for this study and is willing and able to comply with the protocol, including taking study medication, attending required visits and adhering to study procedures.
3. Subject must be able to understand and follow verbal and written instructions.
4. Male or female subject between 18 to 65 years of age (inclusive) at the time of consent.
5. Subject meets DSM-5 criteria for a diagnosis of schizophrenia as established by clinical interview (using the DSM-5 as a reference and confirmed using the Structured Clinical Interview for DSM-5, Clinical Trials Version [SCID-5-CT]). The time since the subject's diagnosis must be ≥ 1 year prior to Screening. Every attempt should be made to obtain medical records or to have correspondence with a previous or current treating provider for the purposes of confirming that the previous course and treatment is consistent with schizophrenia.
6. Subject must have a CGI-S score ≤ 4 at Screening and Baseline.
7. Subject must have a PANSS total score ≤ 80 at Screening and Baseline.
8. Subject is judged to be clinically stable (ie, no evidence of an acute exacerbation of schizophrenia) by the Investigator for at least 8 weeks prior to Baseline.
9. Subject must not have been hospitalized for psychiatric illness for at least 8 weeks prior to Screening.
10. Subject must be judged by the Investigator to be an appropriate candidate for switching current antipsychotic medication due to safety or tolerability concerns and/or insufficient efficacy.
11. Subject is taking an oral antipsychotic and the antipsychotic regimen has been stable for at least 6 weeks prior to Screening. Subjects are permitted to remain on non-prohibited psychotropic medications other than the primary pre-switch antipsychotic that have been part of their ongoing treatment regimen as described in [Section 10.3.1](#).

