- Vital sign parameters (supine and standing systolic blood pressure [SBP], supine and standing diastolic blood pressure [DBP], supine and standing pulse rate, respiratory rate, oral temperature), height, weight, BMI, and waist circumference. For a given subject, the Baseline values for all vital sign parameters, height, weight, BMI, and waist circumference do not have to come from the same assessment; the only exceptions are: (1) the Baseline flag for weight and BMI should be applied to records from the same assessment and it should be the last assessment prior to first dose where weight is available , (2) the Baseline flag for supine SBP and DBP, standing SBP and DBP, and the derived corresponding orthostatic endpoints (i.e., standing SBP – supine SBP; standing DBP – supine DBP) should be applied to records from the same assessment and it should be the last assessment prior to first dose where all four BP measures are available, (3) the Baseline flag for supine and standing pulse rate and the derived corresponding orthostatic endpoint (i.e., standing pulse rate – supine pulse rate) should be applied to records from the same assessment and it should be the last assessment prior to first dose where both pulse rate measures are available.
- ECG parameters: For a given subject, the Baseline values for all ECG parameters do not have to come from the same assessment. Baseline flag does not need to be derived for ECG parameters in the category of “FINDINGS”.
- Nicotine use data: Baseline of this outcome measure should be taken strictly from the assessment given at Visit 1 without regard to its temporal relationship to the first dose of study medication.
- Healthcare resource utilization data: Baseline of this outcome measure should be taken strictly from the assessment given at Visit 2 without regard to its temporal relationship to the first dose of study medication.

The Baseline flag may be derived for additional outcome measures based on the needs during analyses.

Document: PPD

Author: PPD

Version Number:

1.0

Version Date:

06MAY2024

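### Entry criteria close most of the 3-month HCRU look-back to psychiatric admission, so the change from Baseline in schizophrenia-related hospitalizations is pushed toward an apparent increase

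*SAP*

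**What the plan says.** Protocol Table 2, footnote r, sets the reference period: "Baseline will have 3-month lookback period". Protocol 11.5.8 lists what is recorded, including "hospitalizations (total number and number related to schizophrenia) in the previous 3 months", and has the later assessment cover the time since the previous one. SAP 6.2 fixes the source: "Baseline of this outcome measure should be taken strictly from the assessment given at Visit 2".

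The entry rules act on the same calendar time. Inclusion criterion 9 (Protocol 8.1) reads "Subject must not have been hospitalized for psychiatric illness for at least 8 weeks prior to Screening". Inclusion criterion 8 requires "no evidence of an acute exacerbation of schizophrenia) by the Investigator for at least 8 weeks prior to Baseline". Exclusion criterion 4 (Protocol 8.2) removes subjects whose symptoms change to a clinically significant degree between Screening and Baseline. Screening lasts up to 21 days (Protocol 7.1) and may be extended by 7 (Protocol 11.9.1).

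SAP 16.8 and Protocol 15.3.6.1 first summarize hospitalizations per month and average length of stay at Baseline and Week 8, in all-cause and schizophrenia-related versions. They then plan "The change in the number of physician's office visits, ER visits, and hospitalizations, the average length of hospital stays" as changes from Baseline. That change sentence does not repeat the two versions, and it does not say that the counts are per month. The protocol synopsis does put the change in counts on a per-month scale. Neither document mentions the entry criteria in connection with this comparison.

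**The concern.** A before/after difference is readable only if the event could be recorded in both periods on similar terms. Here the subjects were selected for having had no psychiatric admission during most of the before period, and no entry criterion applies to the after period. The Baseline count is held down by selection, so a fall can hardly be seen and a handful of admissions will show as a rise.

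There is no control arm to separate this from an effect of treatment, and Protocol 5.3 words the objective as the impact of the drug on resource use. A reader of the table could take the selection effect for a rise in admissions after the switch. The error would run against the drug.

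**Working it through.** The documents give no admission rate and no precision target for HCRU, so there is no figure of the plan's own to reproduce.

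**Inputs**
- Look-back L: 3 months, taken as 91 days (Table 2 footnote r).
- Closed by criterion 9: 8 weeks = 56 days before Screening.
- Screening interval S: 1, 21 or 28 days. Its closure is inferred from inclusion 8 and exclusion 4, because no criterion names an admission during screening.
- Post-Baseline window: about 56 days, for subjects who complete.
- Schizophrenia-related admissions are treated as psychiatric admissions.

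**Formulas**
- Closed share = (56 + S)/L, and open days = L − 56 − S.
- Let the admission rate be a constant h per day, with no drug effect. The look-back then holds h × open days, and the post-Baseline window holds h × 56.
- Ratio per month (post to Baseline) = L/open days. Ratio of raw counts = 56/open days.

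| Reading | Closed days | Closed share | Open days | Ratio per month | Ratio, raw counts |
|---|---|---|---|---|---|
| Criterion 9 only | 56 | 62% | 35 | 2.6 | 1.6 |
| With 1 day of screening | 57 | 63% | 34 | 2.7 | 1.65 |
| With 21 days | 77 | 85% | 14 | 6.5 | 4.0 |
| With 28 days | 84 | 92% | 7 | 13 | 8.0 |

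Taking 3 months as 90 or 92 days moves the closed share with 21 days of screening to 86% or 84%, and the per-month ratio to 6.9 or 6.1.

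**If the post-Baseline rate is lower.** Each ratio scales with the post-Baseline rate. The apparent rise per month disappears only if that rate falls to open days/L of the earlier rate: 34/91 = 37%, 14/91 = 15% or 7/91 = 8%. On raw counts the break-even is open days/56: 34/56 = 61%, 14/56 = 25% or 7/56 = 12.5%.

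**Absolute size.** Assume 0.2 psychiatric admissions per person-year in the 101 enrolled subjects (SAP 3.4), with full follow-up. Expected after Baseline: 101 × 0.2 × 56/365.25 = 3.1. Expected in the look-back: 1.9 (1-day screening) to 0.4 (28-day screening). At 0.1 per year the figures are 1.5 against 0.9 to 0.2, and at 0.4 per year 6.2 against 3.8 to 0.8.

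**All-cause hospitalizations.** Only the psychiatric share s is closed. The per-month ratio is 1/(1 − s × closed share). At an assumed s = 0.5 this is 1.5 to 1.9. On raw counts the shorter second window pulls down by 56/91 = 0.62. The net result is an increase only if s exceeds 35/(56 + S): 35/57 = 61%, 35/77 = 45% or 35/84 = 42%. The documents do not give s.

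**Length of stay.** Few subjects can have a psychiatric stay in the open days. Neither SAP 16.8 nor SAP 16.10 says how a subject with no stay enters the average or the change. The change is therefore sparse or undefined, and its direction depends on a rule that is not written.

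**The case against.** The strongest reply is that little depends on this row. HCRU is among the other endpoints. Protocol 15.3.6 says that the study is uncontrolled and that no inferential effectiveness statistics will be given. Week 8 values are reported separately, and an error against the drug cannot create a claim of benefit. All of this is true and limits the consequence to a misleading summary. It does not remove the point: a general statement that the study is uncontrolled does not tell a reader that the entry criteria push this number in a known direction.

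Other parts of the reply stand as limits:
- The ratios need a constant rate before and after Baseline, in subjects chosen for stability. A lower later rate shrinks them.
- Closure of the screening interval is inferred. The explicit figure is 62%, which already supports most of the look-back.
- The later window is not wholly unrestricted. Subjects given non-permitted psychotropics for an exacerbation or for lack of efficacy are discontinued (Protocol 10.3.2), as are those with Type 4 or 5 suicidal ideation (Protocol 11.4.6.4). Observation may therefore end early in those most at risk of admission.
- The change sentence does not itself name a schizophrenia-related version. That reading comes from the paragraph before it.

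A reader might go further and infer that the change in all hospitalizations is biased upward, that length of stay is too, or that the HCRU objective cannot be answered at all. The documents do not support this. Criterion 9 concerns psychiatric admission only, and the all-cause direction on raw counts turns on an unstated share. No upward bias in length of stay is shown. Office visits, caregiver hours, employment status and unpaid care are not directly restricted by these criteria.

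**Conclusion.** The point holds for schizophrenia-related hospitalizations. At least 62% of the look-back is closed by an explicit criterion, and 63% to 92% counting screening. The planned change is pushed toward an increase on either scale: about 2.7 to 13 times per month and 1.65 to 8 times on raw counts, with no drug effect. Those sizes rest on a constant admission rate, a 91-day look-back, full follow-up and an admission-free screening interval. The closed 56 days rest on none of the rate assumptions.

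All-cause hospitalizations are affected in part: upward per month, of uncertain direction if raw counts are used. The wording of the change sentence leaves that choice open. This is a fault in one descriptive comparison and does not touch the primary or secondary endpoint.

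**What to change.** In SAP 16.8 and Protocol 15.3.6.1:
- Omit the change from Baseline for schizophrenia-related hospitalizations and for their length of stay. Report instead the post-Baseline number of admissions, the number and percentage of subjects affected, and the rate per person-time. The synopsis already plans the number and percentage of subjects hospitalized by visit, so the SAP can carry that row over.
- State that the change in all-cause hospitalizations is per month, in line with the synopsis.
- Footnote the all-cause hospitalization change and the schizophrenia-related ER change: Baseline is truncated by inclusion criteria 8 and 9.
- Keep the change from Baseline for physician visits and caregiver hours.

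This needs only wording and table shells. No data are lost and no eligibility rule changes. The cost is one descriptive before/after row that could not be interpreted as it stands.
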